Email: [contact]

Co-Investigator

[name]
City of Hope
Dept. of Radiation Oncology
T: [contact]
Email: [contact]

Co-Investigator

[name]
City of Hope
Dept. of Radiation Oncology
T: [contact]
Email: [contact]

Co-Investigator

[name] PhD
City of Hope
Dept. of Radiation Oncology
T: [contact]
Email: [contact]

[figure not shown]
Co-Investigator

[name], PhD
City of Hope
Dept. of Radiation Oncology
T: [contact]
Email: [contact]

Co-Invesitagor

[name]
City of Hope
Dept. of Radiation Oncology
T: [contact]
Email: [contact]

STUDY SCHEMA

PROTOCOL SYNOPSIS

The RefleXion Medical Radiotherapy System (RMRS) is a hybrid imaging-therapy system that is FDA cleared (K190978) to deliver IMRT/SBRT/SRS external beam radiation therapy. It consists of 6 megavoltage (MV) photon radiotherapy delivery, PET imaging hardware, kilovoltage (kV) X-ray CT imaging, and treatment planning subsystems. The system includes the capability of PET imaging when used in a research mode.

Prostate-specific membrane antigen (PSMA) PET with 2-(3-{1-carboxy-5-[(6-[18F]fluoro-pyridine-3-carbonyl)-amino]-pentyl}-ureido)-pentanedioic acid ([18F]-DCFPyL) has been approved for imaging PSMA- positive lesions in men with prostate cancer with either (1) suspected metastasis who are candidates for initial definitive therapy or (2) suspected recurrence based on elevated serum prostate-specific antigen (PSA) level. The RefleXion system is designed to facilitate delivery of biology-guided radiotherapy (BgRT). The system uses PET emissions to guide radiotherapy delivery in real-time and has been studied for use with FDG. In the future, BgRT guided by [18F]-DCFPyL as a biological fiducial carries a potential to improve radiotherapy dose distribution for patients with prostate cancer.

As a requirement for such future evaluation of [18F]-DCFPyL as a biological fiducial, an understanding of the performance of the PET imaging subsystem on the RMRS is needed to correctly detect PET signals derived from [18F]-DCFPyL. Therefore, a single-arm, prospective study to better assess and possibly optimize the performance of the PET imaging subsystem for detection of [18F]-DCFPyL PET signals as a foundation to evaluate [18F]-DCFPyL-based BgRT treatment planning and delivery in future studies is being proposed.

On the day of, and upon completing SOC [18F]-DCFPyL PET-CT, patients will undergo an additional “imaging-only session” on the RefleXion PET-CT (Figure 1). Aside from standard of care (SOC) [18F]-DCFPyL, no PET tracer or other molecule will be administered, and no external-beam radiotherapy will be delivered in this study.

Evidence to be gathered in this study is intended to allow assessment of the technical performance of the PET imaging subsystem on RMRS in patients with prostate cancer undergoing SOC imaging with [18F]-DCFPyL for diagnostic purposes. Evidence from this study will supplement and enhance technical understanding of the [18F]-DCFPyL-guided BgRT delivery. As such, the patient population selected for this investigation is meant to optimally represent the spectrum of cases, with respect to motion and radiographic environment that a radiation oncologist may encounter in practice.

Protocol Title	
A Prospective Study of the RefleXion [18F]- DCFPyL PET-CT Subsystem Imaging Performance in Patients with Prostate Cancer	
Study Detail	
Population/Indication(s):	Patients with prostate cancer who will be undergoing ([18F]-DCFPyL) PET-CT scan
Phase:	pilot
Sample Size:	25 evaluable patients
Estimated Accrual Duration:	18 months
Estimated Study Duration	24 months
Participant Duration:	72 hours
Study Agents:	NA

Study Design

Single arm, prospective study

Objectives

Primary Objective(s)

- To determine the imaging performance of 2-(3-{1-carboxy-5-[(6-[18F]fluoro-pyridine-3-carbonyl)-amino]-pentyl}-ureido)-pentanedioic acid ([18F]-DCFPyL) PET-CT imaging subsystem of the RefleXion Medical Radiotherapy System Device in patients undergoing standard-of-care (SOC) [18F]-DCFPyL PET-CT on the same day.

Endpoints

Primary Endpoint(s):

- To compare imaging performance of the [18F]-DCFPyL PET-CT subsystem on the X1 RMRS to detect lesions (primary and metastatic) in patients with prostate cancer, relative to diagnostic [18F]-DCFPyL PET-CT.

Secondary Endpoint(s):

- Percent of cases where X1 RMRS PET data can be used to generate an acceptable BgRT plan such that dosimetric parameters for the target and the nearby normal anatomy are met based on investigator assessment.

Intervention Description

Baseline Assessments within thirty days prior to the X1 RMRS PET Imaging-only session:

- Demographics & medical history
- SOC diagnostic [18F]-DCFPyL PET-CT
 - Subject weight and height
 - Injected dose and injection time of [18F]-DCFPyL

1.0 OBJECTIVES

1.1 Primary Objective(s)

- To assess imaging performance of the [18F]-DCFPyL PET-CT subsystem on the X1 RMRS to detect lesions (primary and metastatic) in patients with prostate cancer.

1.2 Secondary Objective(s)

- To determine the feasibility of generating a BgRT plan using X1 RMRS-acquired [18F]-DCFPyL PET data derived from the imaging-only session at the studied dose level.

2.0 BACKGROUND

2.1 Overview and Justification for Study Design

2.1.1 [18-F]-DCFPyL PET-CT

Prostate-specific membrane antigen (PSMA) PET with 2-(3-{1-carboxy-5-[(6-[18F]fluoro-pyridine-3-carbonyl)-amino]-pentyl}-ureido)-pentanedioic acid ([18F]-DCFPyL) has been approved for imaging PSMA positive lesions in men with prostate cancer with either primary high-risk prostate cancer with suspected metastasis who are candidates for initial definitive therapy or suspected recurrence based on elevated serum prostate-specific antigen (PSA) level (1).

This approval was based on findings from the CONDOR (2) and OSPREY (3) studies. The multicenter phase 3 CONDOR study included 208 men with biochemical recurrence, defined as rising PSA ≥ 0.2 ng/mL after prostatectomy or ≥ 2 ng/mL above nadir after radiation therapy. A total of 63.9% of patients who had no evidence of disease on conventional imaging had a change in management after [18F]-DCFPyL PET-CT was performed. The disease detection rate was 59% to 66% (at least one lesion detected per patient by [18F]-DCFPyL PET-CT) (2). In the phase 2/3 OSPREY trial, [18F]-DCFPyL PET-CT was assessed in two patient cohorts. Cohort A included men with high-risk prostate cancer undergoing surgery, and the researchers assessed the capacity of [18F]-DCFPyL PET-CT to detect prostate cancer in pelvic lymph nodes. Cohort B included patients with suspected metastatic or recurrent disease, and the researchers examined the performance of [18F]-DCFPyL PET-CT in detecting distant metastases. In cohort A, [18F]-DCFPyL PET-CT detected in the pelvic lymph nodes with a specificity of 97.9%, a sensitivity of 40.3%, and a positive predictive value (PPV) of 86.7%. The sensitivity and PPV rates for detecting metastatic lesions in cohort B were 95.8% and 81.9%, respectively (3). In the OSPREY and CONDOR studies, [18F]-DCFPyL PET-CT was found to be safe and well tolerated (2,3). Another study (4) evaluated 160 patients with high-risk prostate cancer. 56% of the included patients were shown to have metastatic disease based on [18F]-DCFPyL PET-CT, and 17% of patients had a change in management based on the PET-CT findings. Only 1% of patients had to undergo additional imaging because of equivocal findings on the [18F]-DCFPyL PET-CT. Authors concluded that [18F]-DCFPyL PET-CT should be used as first-line imaging modality for therapy selection in patients with primary high-risk prostate cancer.

2.1.2 RefleXion Medical Radiotherapy System and biology-guided radiotherapy

The RefleXion Medical Radiotherapy System (RMRS) is a hybrid imaging-therapy system that is FDA cleared (K190978) to deliver IMRT/SBRT/SRS external beam radiation therapy. It consists of 6 megavoltage (MV) photon radiotherapy delivery, PET imaging hardware, kilovoltage (kV) X-ray CT imaging, and treatment planning subsystems. The system includes the capability of PET imaging when used in a research mode.

It is hypothesized that BgRT guided by [18F]-DCFPyL as a biological fiducial may improve radiotherapy dose distribution for patients with prostate cancer. As a requirement for such evaluation of [18F]-DCFPyL as a biological fiducial, the performance of the PET imaging subsystem on the X1 RMRS to correctly detect PET signals derived from [18F]-DCFPyL, needs to be better understood. Therefore, a single-arm, prospective study to better assess and possibly optimize the performance of the PET imaging subsystem for detection of [18F]-DCFPyL PET signals as a foundation to evaluate [18F]-DCFPyL-based BgRT treatment planning and delivery in subsequent studies, is proposed.

On the day of, and upon completing the standard of care (SOC) [18F]-DCFPyL PET-CT, patients will undergo an addition “imaging-only session” on the X1 RMRS PET-CT (Figure 1). No additional PET tracer or any other molecule will be administered, and no therapeutic radiation will be delivered in this study.

The evidence to be gathered in this study is intended to allow assessment of the technical performance of the PET imaging subsystem on the X1 in a clinically relevant situation, namely in patients with prostate cancer undergoing SOC imaging with [18F]-DCFPyL. Long term, the evidence from this study will supplement and enhance technical understanding of the [18F]-DCFPyL-guided BgRT delivery. As such, the patient population selected for this investigation is meant to optimally represent the spectrum of cases, with respect to motion and radiographic environment, that a radiation oncologist may encounter in practice.

[figure not shown]

Figure 1: Study Flowchart

3.0 ELIGIBILITY CRITERIA

Patient MRN (COH Only)

Patient Initials (F, M, L):

Participants must meet all of the following criteria on screening examination to be eligible to participate in the study:

3.1 Inclusion Criteria

- 1. Documented informed consent of the participant and/or legally authorized representative.
- 2. Age: ≥ 21 years
- 3. Patients undergoing SOC [18F]-DCFPyL PET-CT
- 4. Patients should be scheduled for [18F]-DCFPyL PET-CT prior to study entry

3.2 Exclusion Criteria

- 1. Known psychiatric or substance abuse disorder that would interfere with conduct of the study
- 2. Patient weight exceeding the weight limit (450 pounds) outlined per X1 RMRS specifications sheet.

Eligibility Confirmed* by (Choose as applicable):	Print Name	Signature	Date
 Site PI			
 Authorized study MD			
 Study Nurse			
 Study CRA/ CRC			
 Other: _____			

*Eligibility should be confirmed per institutional policies.

4.0 PARTICIPANT ENROLLMENT, ASSIGNMENT

4.1 Pre-Enrollment Informed Consent and Screening Procedures

The informed consent process is to be fully documented (see [Section 13.4](#)), and the prospective participant must receive a copy of the signed informed consent document. Screening procedures are listed in [Section 7.0](#) (Study Calendar).

4.2 Participant Enrollment

Registration of participants will be according to the following steps:

- Prospective participants must complete the informed consent process, including a signed informed consent, prior to proceeding to study screening.
- Once all the pre-study requirements have been fulfilled, including a completed eligibility checklist ([Section 3.0](#)) the study coordinator will register the eligible patient into the OnCore Clinical Trials Management System.
- Patients failing to meet all protocol eligibility criteria, including informed consent, may not be registered for the trial.

4.3 Screen Failures and Registered Participants Who Do Not begin Study Intervention

Notify the study team immediately if the participant screen fails after registration or if the participant does not start intervention.

5.0 STUDY PROGRAM

5.1 Study Plan

SOC [18F]-DCFPyL PET-CT

All SOC [18F]-DCFPyL PET-CT studies should be performed on the Siemens Vision 600 PET-CT machine in the Outpatient Imaging Center (OIC) in the Department of Nuclear Medicine at City of Hope, in accordance with departmental protocol. Patients who demonstrate at least one PET avid site will then have a PET-CT on the RefleXion X1 system. A PET avid site could include the prostate gland or a metastatic site. If no PET avid lesion is seen on the SOC [18F]-DCFPyL PET-CT, then the patient will not have a PET-CT on the RefleXion X1 system.

Imaging-only session on the RefleXion X1 machine

On the day of, and upon completing the standard of care (SOC) [18F]-DCFPyL PET-CT, patients will undergo an addition “imaging-only session” on the RefleXion PET-CT. Site should make every effort to start SOC [18F]-DCFPyL PET-CT scan within 60 minutes of SOC [18F]-DCFPyL injection and subsequently start X1 RMRS scan within 120 minutes post injection (Figure 1). No additional PET tracer or any other molecule will be administered, and no therapeutic radiation will be delivered in this study. See Appendix for additional details of workflow.

Post-image-acquisition transfer of anonymized image data to the Funding Support/Industry Partner will be within one week from the X1 PET scan.

BgRT Planning

Within a week after the X1 RMRS PET scan a BgRT plan will be generated using X1 RMRS-acquired [18F]-DCFPyL PET data derived from the imaging-only session. The percent of cases where X1 RMRS [18F]-DCFPyLPET data can be used to generate an acceptable BgRT plan such that dosimetric parameters for the target and the nearby normal anatomy are met based on investigator assessment will be determined.

5.2 Duration of Study

Enrollment is estimated to occur over twelve to eighteen (12-18) months, and for the total study duration to be approximately eighteen to twenty-four(18-24) months.

5.3 Duration of Study Participation

Study patients can expect to be participants of this study for no longer than 72 hours. Both imaging sessions (SOC [18F]-DCFPyL PET-CT and imaging on X1 RMRS) will take place on the same day, and adverse events assessment will take place within 72 hours after the imaging session.

5.3.1 Withdrawal and Replacement of Subjects

Subjects may withdraw their consent at any time. Subject's withdrawal of consent must be documented. Withdrawn subjects will not undergo any additional follow-up. Patients with imaging results deemed unevaluable will be replaced.

5.4 Sources of Methods of Recruitment

Patients will be recruited from those seen at the Department of Radiation Oncology at City of Hope. After eligibility criteria have been reviewed, eligible patients will be offered the opportunity to participate in the study. A brief description of the study will be given verbally to the patients, followed by written informed consent, and any relevant supplemental material as needed. The patients will be given ample time to review the consent and a time for questions and answers will be provided. No financial incentives will be provided to the patients.

6.0 ANTICIPATED ADVERSE EVENTS

Subjects will undergo localization (positioning) scans with the X1 RMRS integrated fan-beam kVCT imaging prior to the PET image collection session. Effectively, the only extra dose (on top of SOC [18F]-DCFPyL PET-CT scan) will be coming from this kVCT. A significant increase in subjects' risk with this additional imaging session is not expected. For a single additional kVCT scan with the X1 RMRS, the extra effective dose a patient could receive usually ranges between 10-15 mSv, or 1.0-1.5 cGy. Based on the established clinical literature (5,6,7), the degree of risk for populations of this additional low dose is unclear and controversial, but the risk for any one individual is remote. Study subjects will continue to receive standard of care treatments throughout the study, which are not part of these study procedures.

Appropriate clinical assessments will be performed as indicated to identify all AEs. AEs will be graded according to the NCI Common Terminology Criteria for Adverse Events (CTCAE) version 5. Signs and symptoms of existing disease progression will not be considered AEs.

7.0 STUDY CALENDAR

Assessments	Baseline*	Day 0	Follow-up^
Informed Consent	X		
Demographics	X		
Medical History	X		
Height/Weight	X		
SOC [18F]-DCFPyL PET-CT		X	
X1 PET Imaging-only session		X	
Toxicity Collection			X

*Within thirty days prior to the X1 PET Imaging-only session:

^Within 72 hours of completion of X1 RMRS PET Imaging-only session: Adverse Events assessment by using Common Terminology Criteria for Adverse Events (CTCAE) v5

8.0 ENDPOINT DEFINITIONS/MEASUREMENT OF EFFECT

8.1 Primary Endpoint

To compare imaging performance of the [18F]-DCFPyL PET-CT subsystem on the X1 RMRS to detect lesions (primary and metastatic) in patients with prostate cancer with the diagnostic [18F]-DCFPyL PET-CT.

8.2 Secondary Endpoint(s)

Percent of cases where X1 RMRS [18F]-DCFPyL PET data can be used to generate an acceptable BgRT plan such that dosimetric parameters for the target and the nearby normal anatomy are met based on investigator assessment.

9.0 STATISTICAL CONSIDERATIONS

9.1 Study Analysis/Statistics

This study will compare the performance of the [18F]-DCFPyL PET-CT subsystem on the RefleXion X1 system to detect selected lesions in patients with prostate cancer with the SOC diagnostic [18F]-DCFPyL PET-CT.

One key metric will be the percent of patients with lesions identified on SOC PET-CT that are not identified on X1 (false negatives if considering SOC the true standard). While patients will not have their SOC scan evaluated prior to X1, we anticipate at least 50% will have positive lesions identified on SOC in our patient population. With 12 patients with SOC detected lesions, there is at least 14% chance of finding a false negative if the true false negative rate is 15%, and 93% of observing a false negative if the true false negative rate is 20%.

For the SOC [18F]-DCFPyL PET-CT, the maximum SUV and the greatest dimension in centimeters will be recorded for each PET avid malignant lesion identified by the nuclear medicine radiologist. The

patient's radiation oncologist will interpret the X1 PET scan for the same metrics. Any discordances will be documented, and the final disposition recorded after a discussion between the radiation oncologist and the nuclear medicine radiologist.

Graphical presentations will be provided to compare SOC positive lesions and X1 positive lesions, and SOC positive lesions and X1 negative lesions with regards to lesion size, lesion location (bone, lymph nodes, soft tissue, visceral organ) and SUV uptake.

The true positive lesions identified on the X1 PET images will be identified and used for BgRT planning. For the secondary endpoint, simulated planning using the RefleXion treatment planning software will be performed, and the radiation dose to organs at risk calculated. Principal investigator will determine whether this plan is acceptable or not. The percent of cases in which RefleXion [18F]-DCFPyLcPET data led to an acceptable plan will be recorded (descriptive statistics).

Because this is an exploratory study, descriptive statistics will be utilized to quantify results. Mean, standard deviation, IQR, and range will be reported for each continuous variable. Frequency and percentage will be reported for categorical variables. Statistical significance will be assessed at the 0.05 level, one-sided.

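### The key false-negative metric counts patients but its event is missed lesions, with no any-or-all rule; a lesion-level miss rate with an interval clustered by patient should be reported beside it, and the printed 14% should read 86%.

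*Combined protocol and SAP*

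**What the plan says.** Section 9.1 (Study Analysis/Statistics) names as one key metric the "percent of patients with lesions identified on SOC PET-CT that are not identified on X1". It treats the SOC scan as the reference, calling these "false negatives if considering SOC the true standard". The sizing statement follows: "With 12 patients with SOC detected lesions, there is at least 14% chance of finding a false negative" at a true rate of 15%, and a 93% chance at a true rate of 20%. It does not say whether those rates are per patient or per lesion.

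The data are collected lesion by lesion. In Section 9.1, for the SOC scan, "the maximum SUV and the greatest dimension in centimeters will be recorded for each PET avid malignant lesion", and the X1 scan is read for the same measures. Discordances are documented and resolved by discussion. SOC-positive lesions that X1 finds and those that it misses are compared in graphs by size, location and SUV. The Appendix has a contour made for every lesion selected for X1 imaging, and Section 5.1 requires at least one avid site. Several lesions per patient are therefore possible, but no mean, maximum or distribution is given.

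Sections 1.1 and 8.1 frame the objective and primary endpoint as detection of lesions. Neither gives a counting rule.

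**The concern.** A patient with three SOC lesions, two seen on X1 and one missed, is a false negative on one reading of the metric and not on the other. The plan does not choose, so the choice could be made after the data are seen.

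Settling the definition would not be enough. With scanner sensitivity per lesion held fixed, the any-miss percentage rises with the number of lesions per patient and the all-missed percentage falls, unless misses within a patient are perfectly correlated. Either figure on its own mixes how well X1 detects a lesion with how many lesions these patients have. The objective asks about the first of these. Section 9.1 names no lesion-level rate and no interval.

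The sizing statement has a related weakness. Its rates have no stated unit, and one of its two probabilities is wrong on any reading.

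**Working it through.** **Inputs from the documents.** 12 SOC-positive patients; true false-negative rates of 15% and 20%; stated chances of at least 14% and 93% (all Section 9.1).

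**Assumptions.** The documents give neither the number of lesions per patient, k, nor the within-patient correlation of misses, r. I use k = 1, 2, 3 and r = 0 or 0.3, with every patient having the same k.

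**Step 1: the plan's own figures.** With one yes/no result per patient at rate p, the chance of at least one false negative in 12 patients is 1 − (1 − p)^12.

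- p = 0.20: 1 − 0.80^12 = 1 − 0.0687 = 0.931. The stated 93% reproduces.
- p = 0.15: 1 − 0.85^12 = 1 − 0.1422 = 0.858. The stated 14% does not reproduce. It equals 0.85^12, the chance of no false negative. The matching figure is 86%.

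**Step 2: the two readings.** Let q be the lesion miss rate. With independent lesions, any-miss = 1 − (1 − q)^k and all-missed = q^k. For two lesions with correlation r, all-missed = q² + r·q(1 − q) and any-miss = 2q − all-missed. With q = 0.15 and r = 0.3, all-missed = 0.0225 + 0.3 × 0.1275 = 0.0608 and any-miss = 0.30 − 0.0608 = 0.239. The three-lesion row with r = 0.3 is from a beta-binomial model.

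| Lesions per patient | r | Any-miss, q = 15% | All-missed, q = 15% | Ratio |
|---|---|---|---|---|
| 1 | – | 15.0% | 15.0% | 1 |
| 2 | 0 | 27.8% | 2.3% | 12.3 |
| 2 | 0.3 | 23.9% | 6.1% | 3.9 |
| 3 | 0 | 38.6% | 0.3% | 114 |
| 3 | 0.3 | 30.1% | 3.3% | 9.1 |
| any | 1 | 15.0% | 15.0% | 1 |

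At q = 20% with independent lesions, the pairs are 36.0% and 4.0% for two lesions (ratio 9) and 48.8% and 0.8% for three (ratio 61).

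**Step 3: what this does to the sizing statement.** If 15% and 20% are patient-level rates, Step 1 holds for any number of lesions: 85.8% and 93.1%. If they are lesion-level rates, the chance of a false negative among 12 patients depends on the reading. At 20% with three independent lesions it is 1 − (1 − 0.488)^12 = 99.97% for any-miss and 1 − (1 − 0.008)^12 = 9.2% for all-missed, against the stated 93%.

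**The case against.** The strongest reply is that this is an exploratory pilot with descriptive statistics and no success threshold on this metric. A patient-level miss percentage is a legitimate summary, and a lesion-level rate is not free of case mix: it depends on lesion size, site and uptake, and gives more weight to patients with many lesions. All of that stands. It limits the consequences, but a descriptive metric still needs a counting rule, and the stated objective is lesion detection.

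A reader might also infer four stronger things that the documents do not support.

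- *That the two readings differ about 100-fold.* That takes three independent lesions in every patient at a 15% miss rate. The documents give none of the lesion counts. Lesions in one patient share a scan and tracer timing, so correlated misses are plausible; at r = 0.3 the ratio is about 4 at two lesions and 9 at three.
- *That the sizing figures hold only at one lesion per patient.* Read as patient-level rates, which fits a count of 12 patients, the calculation holds for any lesion count. Conversely, the 14% is wrong even at one lesion.
- *That the lesion data are discarded.* They are recorded, adjudicated and plotted. Section 9.1 also promises frequencies and percentages for categorical variables in general. What is missing is a named lesion-level rate with an interval.
- *That a lesion-level analysis is simply more precise.* The patient-level and lesion-level rates are different quantities, so comparing their interval widths at a common 15% does not show this.

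**Conclusion.** The point holds. The key metric pairs a patient denominator with a lesion event and gives no rule for patients in whom only some lesions are missed. The gap between the readings runs from nothing (one lesion, or perfectly correlated misses) to about 4-fold to 12-fold at two lesions, and more at three, at an assumed 15% lesion miss rate. The lesion counts and correlations are my assumptions, so the actual gap is unknown until the lesion distribution is seen.

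This is more than a missing definition: either patient-level percentage taken alone mixes scanner sensitivity with lesion burden, and the data for a lesion-level rate are already collected. It should be fixed but does not threaten the study. The correction of 14% to 86% depends on none of these assumptions beyond the plan's 12 patients and 15% rate.

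**What to change.** In Sections 8.1 and 9.1:

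- Report the lesion-level miss rate among SOC-positive lesions that were imaged on X1. The restriction matters because the Appendix has lesions selected for X1 imaging; without it, a lesion never imaged could count as a miss.
- Give a 95% confidence interval that allows for clustering by patient and suits few clusters and few or zero misses. One option is a Wilson or exact interval on the number of lesions divided by the design effect, with the correlation fixed in advance for the case where misses are too few to estimate it. Another is GEE with a small-sample correction, if there are enough misses to fit it. A plain cluster bootstrap has zero width when no lesion is missed.
- Report the patient-level any-miss and all-missed percentages beside it, on the same set of lesions, with the number of lesions per patient.
- State that the 15% and 20% rates are patient-level, with one prespecified yes/no result per patient, and name which result.
- In the same sentence, change 14% to 86%.

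The cost is wording and a little more analysis; no new patients or data are needed. The interval will be wider than one treating lesions as independent: with three lesions per patient and r = 0.3, the design effect is 1 + 2 × 0.3 = 1.6, or about √1.6 = 1.26 times the width. The lesion-level rate gives more weight to patients with many lesions, which is why the patient-level figures should stay beside it.

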9.3 Sample Size, Accrual Rate and Study Duration

- **Total accrual:** We will accrue a maximum of 25 evaluable participants
- **Accrual rate:** Accrual is expected to be completed in 12 months.
- **Study duration** is expected to be about 18 months.
- **Participant duration** will be about 72 hours

This study is designed to enroll up to 25 evaluable patients, and criteria for patient selection are outlined above. This sample size was determined a priori to represent a sufficient number of patients for a pilot study to evaluate PSMA-positive lesions to describe imaging performance of the [18F]-DCFPyL PET-CT subsystem on the RefleXion X1 system across a spectrum of clinical scenarios.

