APPENDIX

The following describes the general workflow:

- For patients who have SOC imaging within 6 weeks prior to SOC [18F]-DCFPyL PET-CT, suspicious lesion(s) should be identified prior to [18F]-DCFPyL PET-CT.
- Upon completion of SOC [18F]-DCFPyL PET-CT, the images are loaded into the contouring system (e.g., Eclipse, MIM).
- The radiation oncologist identifies the lesion(s) on the SOC [18F]-DCFPyL PET-CT to be imaged on X1 RMRS. Ideally PET-positive lesions should be between 1-5 cm although PET-positive lesions < than 1 cm are acceptable.
- If no lesion is identified, the patient will be informed that he will not need to undergo imaging on X1 RMRS. This patient will be non-evaluable for this study.
- A basic contour of PTV and BTZ is created for each lesion identified. The PTV should be at least 1 cm in diameter. The BTZ should add 10 mm or more depending on the anticipated amount of target motion for each lesion. A dummy OAR is also created.

- Load the CT and contour(s) into X1 RMRS.
- Create an image-only plan with patient reference point (laser confirmation) (to be done by the physicist).
- Safely position the patient onto X1 table, head first, supine: as comfortable and as close to the SOC [18F]-DCFPyL PET-CT position as possible.
- A kVCT localization followed by PET acquisition is then performed on the X1 RMRS.
- Prioritize pelvic lesion(s) first, before bladder accumulates activity, and low SUV lesions first.
- Safely remove the patient from the X1 RMRS.

The estimated time for steps on the X1 RMRS is as follows:

- Loading Patient onto Couch: 5 mins
- Patient Setup: 5 - 10 mins
- Confirming Laser and Move to Scan: 3 mins
- kVCT scan: 3 - 5 mins
- Imaging-only PET scan (depending on scan length): 20 - 35 mins
- Unloading patient from couch: 5 mins
- TOTAL TIME: 40 - 65 mins

Detailed Timeline

Time Point (min)	Nuc Med Tech	CRN	Rad Onc MD	Physicists and technologists
0	Infuse of ptylafir	Notify X1, physicist and rad onc MD		
60	Scan starts	Notify X1, physicist and rad onc MD		
90	Scan ends Images moved to PACS (10-20min)	Notify X1, physicist and rad onc MD Transport patient	Scans reviewed and lesion(s) selected Contours added	
105		Patient arrives in Rad Onc		Load the CT and contour(s) into X1 RMRS.X1 system Create an image-only plan with patient reference point (laser confirmation)

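### Section 9.1 assumes an unread SOC scan and 12 SOC-positive patients, but section 5.1 and the Appendix make every evaluable patient SOC-positive (up to 25), so its false-negative probabilities use the wrong denominator

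*Combined protocol and SAP*

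**What the plan says.** Section 9.1 names as a key metric the percentage of patients whose SOC-identified lesions are missed on X1, with SOC taken as the standard. It says of the design: "While patients will not have their SOC scan evaluated prior to X1, we anticipate at least 50% will have positive lesions identified on SOC". For 12 SOC-positive patients it then claims that "there is at least 14% chance of finding a false negative if the true false negative rate is 15" per cent, and it gives 93% for a true rate of 20%.

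Other sections describe the workflow differently:

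- Section 5.1 sends patients with at least one avid site on SOC to X1. It adds: "If no PET avid lesion is seen on the SOC [18F]-DCFPyL PET-CT, then the patient will not have a PET-CT on the RefleXion X1 system".
- The Appendix has the radiation oncologist pick out and contour lesions on the SOC images before X1. Of a patient with no lesion it says: "This patient will be non-evaluable for this study".
- The Appendix timeline puts SOC review and lesion selection in the 90-minute row and the X1 session at 120 minutes.
- Sections 5.3.1 and 9.2 replace patients whose imaging is unevaluable.
- Section 9.3 says: "We will accrue a maximum of 25 evaluable participants".

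**The concern.** Two designs are described. In section 9.1, patients go to X1 with the SOC scan unread, and about half turn out to be SOC-positive. In section 5.1 and the Appendix, a positive SOC finding is the condition for X1, and a patient without one does not count towards the sample. Both cannot be followed.

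At stake are the only operating characteristics the plan gives for its key metric. Under the workflow, the 50% does not determine how many patients enter the metric. It determines how many must have the SOC scan to yield the evaluable sample. The population also changes: with no SOC-negative patient imaged on X1, a reader of section 9.1 could expect a patient-level specificity that the study cannot provide.

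**Working it through.** **Inputs.** From section 9.1: 12 SOC-positive patients, true false-negative rates of 15% and 20%, printed chances of 14% and 93%, and SOC positivity of at least 50%. From section 9.3: up to 25 evaluable. The plan does not say where 12 comes from. 0.50 × 25 = 12.5 makes half of 25 the likely source, but that is an inference.

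**Step 1: reproduce the printed figures.** The chance of at least one false-negative patient among n is 1 − (1 − p)^n.

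- n = 12, p = 0.20: 1 − 0.80^12 = 1 − 0.0687 = 0.931. The printed 93% is reproduced.
- n = 12, p = 0.15: 1 − 0.85^12 = 1 − 0.1422 = 0.858. The printed 14% is not reproduced. It equals 0.85^12, the chance of seeing no miss.

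Treating 25 patients as unselected, each with a 50% chance of being SOC-positive, does not rescue the 14%: 1 − (1 − 0.5 × 0.15)^25 = 0.858 and 1 − (1 − 0.5 × 0.20)^25 = 0.928.

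**Step 2: find the denominator under the workflow.** X1 requires an avid SOC lesion (5.1). A patient without a lesion is non-evaluable (Appendix). Unevaluable patients are replaced (5.3.1, 9.2). Up to 25 evaluable patients are accrued (9.3). So each evaluable patient is SOC-positive, and n is up to 25.

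**Step 3: recompute.** The last row is the one-sided 95% upper bound on the false-negative rate if no patient is missed, 1 − 0.05^(1/n).

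| | n = 12 | n = 25 |
|---|---|---|
| At least one miss, true rate 15% | 85.8% | 1 − 0.0172 = 98.3% |
| At least one miss, true rate 20% | 93.1% | 1 − 0.0038 = 99.6% |
| Upper bound with zero misses | 22.1% | 11.3% |

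The plan states no such bound; it is added here to show the size of the change.

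**Step 4: number to consent.** At 50% positivity, 25 / 0.50 = 50. Because the plan says at least 50%, this is the upper end of the expected number. The detection rate of 59% to 66% cited in section 2.1.1 would give 25 / 0.66 = 37.9 to 25 / 0.59 = 42.4, or about 38 to 42. Applying it here is an assumption: that study enrolled men with biochemical recurrence, whereas this trial takes any patient having the SOC scan.

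**The case against.** The sponsor has several fair replies.

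**Unread may mean not formally read.** The nuclear medicine report could follow X1, with only the radiation oncologist looking beforehand. That would soften the first clause, but section 5.1 still makes X1 conditional on an avid SOC finding, so a 50% positive share among patients imaged on X1 remains impossible. Applying the 50% to everyone enrolled does not help either, because section 9.3 counts evaluable patients and the Appendix excludes SOC-negative ones.

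**25 is a ceiling.** This stands. The radiation oncologist selects lesions for X1, while section 9.1 has the nuclear medicine radiologist identify the malignant lesions for analysis. If the two disagree, the denominator could fall below 25.

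**The sample size does not rest on the 12.** This also stands. Section 9.3 justifies 25 on pilot grounds, the analysis is descriptive, and no decision threshold depends on these probabilities. The planned graphics in section 9.1 start from SOC-positive lesions, so they already fit the selected cohort.

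A reader might infer three stronger points that the documents do not support:

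- **That the study is too small for this metric.** The correction runs the other way, since 25 informative patients tell more about misses than 12.
- **That accrual time is understated.** No number to consent, consent rate or clinic throughput is given, so the stated period cannot be shown to be short. The differing accrual periods (12 months in 9.3, 12 to 18 in 5.2, 18 in the synopsis) are a separate matter.
- **That section 9.1 promises a blinded X1 read.** Its sentence concerns evaluation of SOC before X1. It says nothing about what the X1 reader knows.

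**Conclusion.** The contradiction is real, and section 9.1 is the outlier against section 5.1, the Appendix workflow and the timeline. If that workflow governs, the stated probabilities have the wrong denominator: the values become 98.3% and 99.6% at 25 evaluable patients. The zero-miss upper bound would be 11.3% rather than 22.1%. Separately, the printed 14% is wrong even for 12 patients, where the value is 85.8%.

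These figures assume the full 25 are reached, that all are SOC-positive on the read used for analysis, and that patients are independent with a common false-negative rate. With fewer than 25 but more than 12, the values lie between the two columns.

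The practical consequences are a misdescribed design, an unstated number to consent, and a population limited to SOC-positive patients, in whom patient-level specificity cannot be estimated. The information on misses is greater than section 9.1 suggests.

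**What to change.** Decide which description is intended and make the sections agree.

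If section 5.1 and the Appendix govern:

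- In 9.1, remove the clause saying SOC is not evaluated before X1. State that X1 is done only after an avid SOC lesion is found, so evaluable patients (up to 25) are SOC-positive.
- In 9.1, replace both printed probabilities with 98.3% (true rate 15%) and 99.6% (true rate 20%) for n = 25. Optionally add the zero-miss upper bound of 11.3%.
- In 9.3, use the 50% only as a planning assumption for consent: up to about 50 consented for 25 evaluable, fewer if positivity is higher.
- State that patient-level results apply to SOC-positive patients and that patient-level specificity will not be estimated.

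This costs wording in sections 9.1 and 9.3, with no extra evaluable patients and no new procedures. The consent figure, now absent, would become visible.

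If section 9.1 is the intended design, the conditions in 5.1, the Appendix evaluability rule and the meaning of 25 evaluable in 9.3 must change instead, which is a larger amendment. If 12 SOC-positive patients remain the basis, the figures to print are 85.8% and 93.1%.
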